8.7.2. Unadjusted comparison of OS between treatment groups

OS will be defined as described in Section 8.3. OS will be summarized for each treatment group (i.e., ENCO+BINI [pooled across COLUMBUS and Flatiron EHR], DAB+TRAM and VEM+COBI). An unadjusted comparison of OS across treatment groups will be conducted using Kaplan-Meier (KM) analyses. OS over time in these treatment groups will be plotted and compared using a log-rank test, with median survival time and survival proportions reported at selected time points (e.g., 6 months, 1 year, 2 years). Hazard ratios for OS comparing ENCO+BINI relative to DAB+TRAM and VEM+COBI will be estimated based on a univariable Cox proportion hazards model. The proportional hazards assumption will be assessed using tests of Schoenfeld residuals. 14

8.7.3. Imputation of missing data on baseline characteristics

Previous analyses of the Flatiron data have found that there are moderate to large amounts of missing data on baseline characteristics such as ECOG performance score and LDH. ¹² As analyses restricted to patients with non-missing data are highly likely to be biased, imputation of missing data on key baseline characteristics is needed to ensure that adjusted analyses of OS between the trial and RWD settings are based on all eligible patients.

In this study, multiple imputation by chained equations (MICE)¹⁵ will be used to impute missing data on baseline characteristics. Briefly, the MICE method imputes data for a missing patient characteristic based on iterative regressions of observed data for that characteristic on observed and imputed values of other baseline characteristics. This process will be repeated for each

characteristic until stable estimates are obtained, and the entire procedure will be repeated so that multiple datasets with imputed values for baseline characteristics are created.

Baseline characteristics to be imputed will include ECOG performance score, LDH, and other clinical or demographic characteristics (e.g., race, BMI, etc.). Additional variables (e.g., age, sex, AJCC diagnosis, time from MM diagnosis to treatment initiation, time from initial diagnosis of melanoma to metastatic disease, number of organs at baseline, metastatic sites, treatments in the therapeutic setting, treatments in the adjuvant setting) will be considered for inclusion in the MICE procedure based on their relevance for adjustment and degree of missingness in the study sample. As recommended in the literature, the MICE approach will be used to create multiple datasets (e.g., 100 datasets) with imputed values, which will be used and combined in subsequent analyses. ¹⁵

Missing data on baseline characteristics will be imputed for all treatment groups. Analyses of baseline characteristics described in Section 8.7.1 will be repeated for each imputed dataset, and then summarized across all imputed datasets.

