8.3. Variables

Table 1 provides a summary of exposure, outcome, and patient baseline characteristics that will be evaluated within the study.

Table 1. Key exposures, outcomes, and patient baseline characteristics

Variable	Role	Data source(s)	Operational definition/categories
Treatment group (ENCO+BINI, DAB+TRAM, VEM+COBI)	Exposure	COLUMBUS trial data; Flatiron EHR	Indicates whether patients initiated ENCO+BINI, DAB+TRAM or VEM+COBI treatment
os	Primary Outcome	COLUMBUS trial data, Flatiron	In the COLUMBUS trial data, defined as the time from the date of randomization to the date of death due to any cause; if death is not observed, patients will be censored at the date of last contact or the data analysis cut-off date (e.g., 15 September 2020), whichever occurs first
	Timaly outcome		In Flatiron EHR, will be defined as the time from the index date to the date of death; patients without a date of death will be censored at their last known activity date (e.g., the last clinical note date) or the end of the follow-up period, whichever occurs first
	COLUMBUS	In the COLUMBUS trial data, defined as the time from the date of randomization to the date of the first documented disease progression or death due to any cause, whichever occurred first; if a patient did not have an event at the analysis cut-off date, PFS will be censored at the date of the last adequate tumour assessment	
PFS	Exploratory Outcome	trial data, Flatiron her	In Flatiron EHR, will be defined as the time from the index date to either the date of first disease progression event or death in the absence of progression; patients without disease progression or death will be censored at the last date the patient could have been assessed for progression (e.g., the last clinical note date) or the data analysis cut-off date (e.g., 30 September 2021), whichever occurs first
Age at baseline (years)	Baseline Characteristic / Potential Confounder	COLUMBUS trial data Flatiron EHR	Patient age; defined at the time of study randomization for COLUMBUS trial data and at the time of treatment initiation for Flatiron EHR
Sex	Baseline Characteristic / Potential Confounder	COLUMBUS trial data; Flatiron EHR	Male, Female, Intersex, or Unknown/Missing

Race	Baseline Characteristic / Potential Confounder	COLUMBUS trial data; Flatiron EHR	Asian, Black, White, Other/Multi-Race, or Unknown/Missing

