Body mass index (BMI) at index	Baseline Characteristic / Potential Confounder	COLUMBUS trial data; Flatiron EHR	Defined as weight (in kg) divided by squared height (in m²)
ECOG at index	Baseline Characteristic / Potential Confounder	COLUMBUS trial data; Flatiron EHR	0, 1, Unknown/Missing; defined during the baseline period of both the COLUMBUS trial data and Flatiron EHR
BRAF mutation status	Baseline Characteristic / Potential Confounder	COLUMBUS trial data; Flatiron EHR	V600E, V600K, Unknown/Missing
AJCC disease stage at initial melanoma diagnosis	Baseline Characteristic / Potential Confounder	COLUMBUS trial data; Flatiron EHR	0, I, II, III, IV, or Unknown/Missing; defined at initial melanoma diagnosis for COLUMBUS trial data and Flatiron EHR
AJCC disease stage at treatment initiation	Baseline Characteristic	COLUMBUS trial data	IIIB, IIIC, IVM1a, IVM1b, or IVM1c; defined at treatment initiation in the COLUMBUS trial data. Not available in the Flatiron EHR
Lactate dehydrogenase (LDH) at index	Baseline Characteristic / Potential Confounder	COLUMBUS trial data; Flatiron EHR	Evaluated in units per liter (U/L) and defined at trial baseline in COLUMBUS trial and during the baseline period in Flatiron EHR
Time from initial melanoma diagnosis to metastatic disease	Baseline Characteristic / Potential Confounder	COLUMBUS trial data; Flatiron EHR	Duration (in months) from melanoma diagnosis to the development of metastatic disease
Time from metastatic melanoma diagnosis to treatment initiation	Baseline Characteristic / Potential Confounder	COLUMBUS trial data; Flatiron EHR	Duration (in months) from metastatic melanoma diagnosis to the initiation of treatment
Year of treatment initiation	Baseline Characteristic	COLUMBUS trial data; Flatiron EHR	Calendar year when treatment was initiated
Region	Baseline Characteristic	COLUMBUS trial data; Flatiron EHR	Europe, North America, Australia, Other, or Missing
Treatment experience in the therapeutic setting	Baseline Characteristic / Potential Confounder	COLUMBUS trial data; Flatiron EHR	Indicates whether patients received targeted therapy as first-line treatment (e.g., Treatment naïve) or as second- line treatment after a prior line of immunotherapy treatment (e.g., Prior 1L IO therapy)

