- For the real-world cohorts, patient baseline characteristics will be obtained from visits ≤3 months prior to the index date, with data from visits closest in time to the index date being used as available. In contrast, in the original analysis plan, to maximize availability of baseline characteristics, the 'baseline' period was allowed to include visits up to 6 months prior to treatment initiation. The decision

to use a stricter definition of baseline here was based on clinical input that certain baseline characteristics of interest (e.g., ECOG PS) are best assessed closest to the index date, despite potential for increased missingness. To address missingness, imputation of baseline characteristics was conducted as described below.

- Key clinical characteristics like ECOG and LDH were missing at baseline for 40-60% of patients in the original study cohort, which would have hampered ability to adjust for potential confounding due to these factors. To address missingness, in this analysis plan we will impute data using multiple imputation by chained equations prior to conducting adjusted analyses. Imputation models will be based on baseline characteristics that would be considered in adjusted models for OS.
- Inverse probability of treatment weighting without any imputation was proposed
 in the original study design to account for baseline differences. Instead, we will
 use multivariable Cox proportional hazards models fit to each of the imputed
 dataset and combine results across all imputations. This approach is preferred as it
 allows us to assess how included covariates are associated with OS in our final
 models, in addition to estimating differences between the treatments of interest.
- Comparisons of OS and PFS will be stratified by first-line and second-line of
 therapy in the original study design. Analyses conducted in this revised analysis
 plan will not be stratified by line of therapy to allow for a larger sample size to
 compare OS and PFS across targeted therapy treatment cohorts. A line of therapy
 variable will be included in Cox proportional hazard models, which can facilitate
 future analyses of comparative effectiveness by line of therapy if required.

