6 HANDLING OF MISSING VALUES

In this study, multiple imputation by chained equations (MICE)¹⁵ will be used to impute missing data on baseline characteristics. Briefly, the MICE method imputes data for a missing patient characteristic based on iterative regressions of observed data for that characteristic on observed and imputed values of other baseline characteristics. This

process will be repeated for each characteristic until stable estimates are obtained, and the entire procedure will be repeated so that multiple datasets with imputed values for baseline characteristics are created.

Baseline characteristics to be imputed will include ECOG performance score, LDH, and other clinical or demographic characteristics (e.g., race, BMI, etc.). Additional variables (e.g., age, sex, AJCC diagnosis, time from MM diagnosis to treatment initiation, time from initial diagnosis of melanoma to metastatic disease, number of organs at baseline, metastatic sites, treatments in the therapeutic setting, treatments in the adjuvant setting) will be considered for inclusion in the MICE procedure based on their relevance for adjustment and degree of missingness in the study sample. As recommended in the literature, the MICE approach will be used to create multiple datasets (e.g., 100 datasets) with imputed values, which will be used and combined in subsequent analyses.¹⁵

Missing data on baseline characteristics will be imputed for all treatment groups.

Analyses of baseline characteristics will be repeated for each imputed dataset, and then summarized across all imputed datasets.

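### The imputation rule names neither treatment group nor data source as a predictor, so a pooled imputation could leave part of the LDH/ECOG confounding in the primary OS hazard ratio

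*Protocol*

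**What the plan says.** Protocol 8.7.3, repeated in SAP 6 and 7.1, describes chained-equations imputation as working "based on iterative regressions of observed data for that characteristic on observed and imputed values of other baseline characteristics". The amendment sections (Protocol 4, SAP 1) give the rule for choosing predictors: "Imputation models will be based on baseline characteristics that would be considered in adjusted models for OS".

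Further candidates are listed as examples, ending with "treatments in the therapeutic setting, treatments in the adjuvant setting) will be considered for inclusion in the MICE procedure". These are earlier treatments, not the index regimen. Protocol Table 1 defines treatment experience in the therapeutic setting by line of therapy: "Indicates whether patients received targeted therapy as first-line treatment", or as second-line treatment after immunotherapy. The index regimen has its own row, classed as the exposure: "Indicates whether patients initiated ENCO+BINI, DAB+TRAM or VEM+COBI treatment". Data source is not a variable in any table. Region and calendar year, which could stand in for source, appear in neither the imputation candidates nor the adjustment list.

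On scope, SAP 6 says "Missing data on baseline characteristics will be imputed for all treatment groups". It does not say whether imputation is pooled or run separately by group or source. On the amount of missing data, SAP 1 says: "Key clinical characteristics like ECOG and LDH were missing at baseline for 40-60% of patients in the original study cohort". That figure comes from a 6-month baseline window, which is now 3 months.

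**The concern.** The analysis model contains treatment group. An imputation model built on the stated rule would not, so it would be poorer than the model it feeds. The gap is lopsided. DAB+TRAM and VEM+COBI come only from Flatiron, where LDH and ECOG are often missing. COLUMBUS required ECOG 0 or 1 at randomization, stratified on it, and defines LDH at trial baseline. In a pooled model with no group or source term, the observed COLUMBUS ENCO+BINI values therefore help to fill the gaps in the comparators. Any difference between the sources that the other predictors do not explain is shrunk, and the Cox model cannot adjust for an imbalance that imputation has partly erased.

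One set of candidate predictors may add to this. Number of organs and metastatic sites are offered for imputation, but Protocol 8.9 says they are very likely underestimated in Flatiron and not comparable with COLUMBUS.

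The primary adjusted OS hazard ratio is at stake. More imputations would not help, and the SAP's optional sensitivity analyses vary covariates and time frames, not the imputation model.

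**Working it through.** The documents give no Flatiron sample size, event count or power, so there is no planned figure to reproduce. The check is by simulation.

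**From the documents:** COLUMBUS ENCO+BINI n = 192; 40% and 60% missing; comparators from Flatiron only; Cox model in each imputed dataset, pooled by Rubin's rules.

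**Assumed:** everything else, as listed below.

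**Step 1. Who supplies the observed values.** Suppose COLUMBUS is complete and Flatiron totals 200 to 600 patients (assumed). The COLUMBUS share of observed LDH values is 192 / (192 + Flatiron observed).
- 200 patients, 60% missing: 192 / (192 + 80) = 71%.
- 600 patients, 40% missing: 192 / (192 + 360) = 35%.

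**Step 2. Effect on the HR, with LDH and ECOG both imputed.** Assumed: groups in the ratio 192 COLUMBUS ENCO+BINI : 60 Flatiron ENCO+BINI : 350 DAB+TRAM : 80 VEM+COBI, scaled up 20-fold to show bias; missing completely at random in Flatiron and none in COLUMBUS; true HR 1; HR 2.0 for LDH>ULN and 1.6 for ECOG 1; ECOG 1 prevalence (COLUMBUS/Flatiron) 29/29, 29/40, 29/45 and 40/29% in the four LDH cases in turn. Entries are the HR for ENCO+BINI vs DAB+TRAM divided by the HR from the same data before deletion. Values below 1 favour ENCO+BINI. There were 8 replicates; the Monte Carlo SE for the imputed analyses is 0.001-0.004.

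| LDH>ULN, COLUMBUS / Flatiron | Missing | Unadjusted | Plan's rule | + treatment and source | + outcome only | All terms |
|---|---|---|---|---|---|---|
| 30 / 30% | 40% | 1.001 | 1.021 | 1.020 | 0.999 | 1.001 |
| 30 / 30% | 60% | 1.001 | 1.025 | 1.024 | 1.000 | 0.999 |
| 30 / 40% | 40% | 0.918 | 0.991 | 1.002 | 0.989 | 1.001 |
| 30 / 40% | 60% | 0.918 | 0.976 | 0.990 | 0.977 | 0.995 |
| 30 / 50% | 40% | 0.854 | 0.965 | 0.980 | 0.978 | 0.999 |
| 30 / 50% | 60% | 0.849 | 0.938 | 0.961 | 0.955 | 0.999 |
| 40 / 30% | 40% | 1.091 | 1.057 | 1.043 | 1.016 | 1.004 |
| 40 / 30% | 60% | 1.098 | 1.082 | 1.065 | 1.022 | 1.000 |

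Outcome means the event indicator plus the Nelson-Aalen hazard. Only ENCO+BINI spans both sources, so treatment plus source is the same as one four-level factor.

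- Where the sources differ, the plan's rule is off by 0.9% (0.991) to 8.2% (1.082). This includes the effect of leaving out the outcome.
- To isolate treatment and source, use the outcome-only column. The confounding left is ln(outcome-only ratio) / ln(unadjusted ratio): lowest ln 0.989 / ln 0.918 = 13%, highest ln 0.955 / ln 0.849 = 28%.
- In the 30/50%, 60% missing case, the plan's rule pulls LDH>ULN prevalence in DAB+TRAM from 50% to 44.8%.
- With equal distributions, adding treatment and source changes nothing. The 2% shift there comes from omitting the outcome.

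**Step 3. A second simulation at realistic size, LDH only.** Assumed: 192 COLUMBUS and 60 Flatiron ENCO+BINI, 300 DAB+TRAM, 100 VEM+COBI; true HR 1. Entries are log-HR bias.

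| COLUMBUS / Flatiron LDH>ULN, LDH HR, missing | Outcome, no factor | Factor, no outcome | Within treatment group, with outcome |
|---|---|---|---|
| 30 / 45%, 2.0, 40% | -0.013 | -0.007 | +0.004 |
| 30 / 45%, 2.0, 60% | -0.025 | -0.014 | +0.005 |
| 25 / 50%, 2.0, 60% | -0.043 | -0.036 | +0.010 |
| 25 / 50%, 2.5, 70% | -0.066 | -0.050 | +0.016 |

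With factor and outcome together, the bias is at most 0.004 in absolute value. At 30/30% it is -0.002 with or without the factor. The SE of the log-HR is about 0.11, so the first two rows are 0.013/0.11 = 0.12 and 0.025/0.11 = 0.23 of an SE, and the worst row is 0.066/0.11 = 0.6.

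**The case against.** **The plan is silent; it does not exclude.** A reader might infer that the plan bars treatment and source. It does not. The sentence on regressions is a brief general account of the method, the candidate lists are examples, and they include metastatic sites, which Protocol 8.9 rules out for adjustment, so the imputation list is not strictly the adjustment list. Pooling is also an inference. All of this stands, and the point is therefore conditional. What remains is that the only stated rule draws predictors from baseline characteristics, and a programmer following it would leave both terms out.

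**Imputing within treatment group would help.** One might think it useless because ENCO+BINI mixes both sources. That is not so. It removes COLUMBUS donors from both comparators and, in Step 3, about 70-80% of the bias (for example -0.066 becomes +0.016). A smaller bias of the opposite sign remains, through Flatiron ENCO+BINI patients with missing values. The plan does not state this approach either.

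**The factor alone is not a cure.** This stands. Without the outcome it leaves ratios of 0.961 to 1.065 in Step 2.

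**Size and direction are unknown.** This stands too. The documents give no LDH or ECOG distributions by source, and SAP 3.2 says the study is not powered for formal testing. The largest Step 3 figure needs a 25-point LDH gap, an LDH HR of 2.5 and 70% missing together.

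**ECOG may drop out.** Both documents require ECOG 0 or 1 at index. If that excludes missing ECOG, the point rests on LDH alone. However, Table 1 keeps an unknown category and 8.7.3 imputes ECOG.

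**Conclusion.** The concern holds in conditional form. The plan bases imputation on baseline characteristics and names neither treatment group nor source. If a pooled imputation follows that rule, and LDH or ECOG differs between COLUMBUS and Flatiron given the other predictors, part of the confounding stays in the primary HR. In the assumed scenarios the rule as written shifts the HR by about 1-8%; with the outcome included, omitting treatment and source still leaves 13-28% of the LDH/ECOG confounding in Step 2.

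A reader might go further and conclude that the primary HR is biased towards ENCO+BINI. The documents do not support that: the sign reverses if COLUMBUS patients have the worse prognosis, and omitting these terms does no harm if the sources do not differ. The figures rest on assumed group sizes, prevalences and effects, near-complete COLUMBUS data and, in Step 2, values missing completely at random in Flatiron. The bias is systematic but mostly a fraction of a standard error. It should be fixed because the remedy is cheap and specific; it does not invalidate the design.

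**What to change.** In Protocol 8.7.3 and SAP 6 and 7.1, state that every imputation model includes:
- a four-level factor: COLUMBUS ENCO+BINI, Flatiron ENCO+BINI, Flatiron DAB+TRAM, Flatiron VEM+COBI;
- the OS event indicator and the Nelson-Aalen cumulative hazard.

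Amend the sentence "Imputation models will be based on baseline characteristics that would be considered in adjusted models for OS" in SAP 1, and its counterpart in Protocol 4, to match. Both elements are needed: together they bring the HR to 0.995-1.004 of the full-data value in Step 2.

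The cost is a sentence or so per document and a few extra predictors in the imputation code, plus a rerun if the models have already been fitted. There is a small loss of precision: in the worst Step 3 scenario the SE rose from 0.112 to 0.120. The Flatiron ENCO+BINI cohort was judged too small for adjusted analysis on its own, so that level may rest on few observed values. Report the number of observed LDH and ECOG values at each level.

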- For the real-world cohorts, patient baseline characteristics will be obtained from visits ≤3 months prior to the index date, with data from visits closest in time to the index date being used as available. In contrast, in the original protocol, to maximize availability of baseline characteristics, the 'baseline' period was allowed to include visits up to 6 months prior to treatment initiation. The decision to use a stricter definition of baseline here was based on clinical input that certain baseline characteristics of interest (e.g., ECOG PS) are best assessed closest to the index date, despite potential for increased missingness. To address missingness, imputation of baseline characteristics was conducted as described below.

- Key clinical characteristics like ECOG and LDH were missing at baseline for 40-60% of
 patients in the original study cohort, which would have hampered ability to adjust for
 potential confounding due to these factors. To address missingness, we will impute data
 using multiple imputation by chained equations prior to conducting adjusted analyses.
 Imputation models will be based on baseline characteristics that would be considered in
 adjusted models for OS.
- Inverse probability of treatment weighting without any imputation was proposed in the
 original study design to account for baseline differences. Instead, we will use
 multivariable Cox proportional hazards models fit to each of the imputed dataset and
 combined results across all imputations. This approach is preferred as it allows us to
 assess how included covariates are associated with OS in our final models, in addition to
 estimating differences between the treatments of interest.
- Comparisons of OS and PFS were stratified by first-line and second-line of therapy in the
 original study design. Analyses conducted in this revised protocol will not be stratified by
 line of therapy to allow for a larger sample size to compare OS and PFS across targeted
 therapy treatment cohorts. A line of therapy variable will be included in Cox proportional
 hazard models, which can facilitate future analyses of comparative effectiveness by line
 of therapy if required.

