Appendix Table 3: Unadjusted and adjusted hazard ratios comparing OS between treatment groups

Results from adjusted models in Appendix Table 3 will be based on multiple imputation via multivariate imputation by chained equations. Expected adjustment factors are listed below; specific functional forms/categorization of adjustment factors will be based on the data.

	Unadjusted model	Adjusted model
	HR (95% CI)	HR (95% CI)
Treatment group		
DAB+TRAM vs. ENCO+BINI		
(ref)		

VEM+COBI vs. ENCO+BINI	
(ref)	
Adjustment factors	
Age (years)	
Male vs female	
Asian race vs. White	
Other race vs. White	
Unknown race vs. White	
BMI (kg/m²)	
ECOG (1 vs. 0)	
LDH (>ULN vs. ≤ULN)	
Treatment naïve vs. prior 1L	
IO treatment	
Prior IO/chemotherapy (Yes	
vs. No)	
Prior surgery (Yes vs. No)	
Time from initial melanoma	
diagnosis to metastatic disease	
Time from metastatic disease	
to treatment initiation

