5 ENDPOINTS AND COVARIATES

Table 1 provides a summary of the exposure (treatment group) and covariates within the study.

Table 1 Exposure and baseline characteristics

Variable	Operational definition				
Treatment group (ENCO+BINI, DAB+TRAM, VEM+COBI)	Indicates whether patients initiated ENCO+BINI, DAB+TRAM or VEM+COBI treatment				
Age at baseline (years)	Patient age; defined at the time of study randomization for COLUMBUS trial data and at the time of treatment initiation for Flatiron EHR				
Sex	Male, Female, Intersex, or Unknown/Missing				
Race	Asian, Black, White, Other/Multi-Race, or Unknown/Missing				

Body mass index (BMI) at index	Defined as weight (in kg) divided by squared height (in m²)			
ECOG at index	0, 1, Unknown/Missing; defined during the baseline period of both the COLUMBUS trial data and Flatiron EHR			
BRAF mutation status	V600E, V600K, or Unknown/Missing			
AJCC disease stage at initial melanoma diagnosis	0, I, II, III, IV, or Unknown/Missing; defined at initial melanoma diagnosis for COLUMBUS trial data and Flatiron EHR			
AJCC disease stage at treatment initiation	IIIB, IIIC, IVM1a, IVM1b, or IVM1c; defined at treatment initiation in the COLUMBUS trial data. Not available in the Flatiron EHR			
Lactate dehydrogenase (LDH) at index	Evaluated in units per liter (U/L) and defined at trial baseline in COLUMBUS trial and during the baseline period in Flatiron EHR			
Time from initial melanoma diagnosis to metastatic disease	Duration (in months) from melanoma diagnosis to the development of metastatic disease			
Time from metastatic melanoma diagnosis to treatment initiation	Duration (in months) from metastatic melanoma diagnosis to the initiation of treatment			
Year of treatment initiation	Calendar year when treatment was initiated			
Region	Europe, North America, Australia, Other, or Missing			
Treatment experience in the therapeutic setting	Indicates whether patients received targeted therapy as first-line treatment (e.g., Treatment naïve) or as second-line treatment after a prior line of immunotherapy treatment (e.g., Prior 1L IO therapy)			

Prior systemic therapies in the adjuvant	Indicates whether patients previously received systemic therapy (e.g., prior surgery, radiotherapy, immunotherapy, or chemotherapy) before initiating treatment				
setting Prior surgery in the adjuvant setting	Indicates whether patients previously used surgery to reduce/remove tumors as a form of treatment				

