5.1 EFFICACY/EFFECTIVENESS ENDPOINT(S)

Table 2 provides a summary of efficacy/effectiveness endpoints that will be evaluated within the study.

Table 2 Clinical outcomes of interest for efficacy/effectiveness

Variable Operational definition					
OS	In the COLUMBUS trial data, defined as the time from the date of randomization to the date of death due to any cause; if death is not observed, patients will be censored at the date of last contact or the data analysis cut-off date (e.g., 15 September 2020), whichever occurs first				
OS	In Flatiron EHR, will be defined as the time from the index date to the date of death; patients without a date of death will be censored at their last known activity date (e.g., the last clinical note date) or the end of the follow-up period, whichever occurs first				
	In the COLUMBUS trial data, defined as the time from the date of randomization to the date of the first documented disease progression or death due to any cause, whichever occurred first; if a patient did not have an event at the analysis cut-off date, PFS will be censored at the date of the last adequate tumour assessment				
PFS	In Flatiron EHR, will be defined as the time from the index date to either the date of first disease progression event or death in the absence of progression; patients without disease progression or death will be censored at the last date the patient could have been assessed for progression (e.g., the last clinical note date) or the data analysis cut-off date (e.g., 30 September 2021), whichever occurs first				

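### The imputation models are described with baseline predictors only; followed as written, leaving overall survival out pulls the LDH hazard ratio (and ECOG's, if imputed) toward 1

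*Protocol*

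**What the plan says.** Protocol 8.7.3, SAP 6 and SAP 7.1 describe multiple imputation by chained equations (MICE) in the same way: each incomplete characteristic is filled in by "iterative regressions of observed data for that characteristic on observed and imputed values of other baseline characteristics". SAP 1 gives the basis, and Protocol 4 carries the same sentence: "Imputation models will be based on baseline characteristics that would be considered in adjusted models for OS". Further variables "will be considered for inclusion in the MICE procedure based on their relevance for adjustment and degree of missingness in the study sample"; every example given is a baseline variable.

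The documents do not treat OS as a baseline characteristic. Protocol Table 1 is titled "Key exposures, outcomes, and patient baseline characteristics" and gives OS the role of primary outcome and treatment group the role of exposure. The SAP makes the same split: "Table 1 provides a summary of the exposure (treatment group) and covariates within the study", while "Table 2 provides a summary of efficacy/effectiveness endpoints that will be evaluated within the study". Neither document names the death indicator, survival time or a cumulative hazard as an imputation predictor. They are also silent on treatment group and data source as predictors. The statement that values are imputed in all treatment groups says whose data are filled in, not what predicts them.

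LDH and ECOG are both to be imputed and are both in the primary Cox model (Protocol 8.7.4), which is pooled by Rubin's rules. Whether any ECOG value remains to be imputed is unclear. Protocol 8.2.1.2 requires ECOG 0 or 1 at index, 8.2.2 excludes only ECOG 2 or more, and Table 1 keeps a missing category.

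**The concern.** When a covariate is imputed without the outcome, the imputed values carry no information about survival beyond what the other covariates carry. The Cox model then averages a true slope in patients with observed values and a slope near zero in patients with imputed values. The covariate's log-HR is pulled toward zero.

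This matters for three reasons.

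- **Missingness is large.** Protocol 4 and SAP 1 report ECOG and LDH missing for 40-60% of the original cohort under a 6-month baseline window. The window is now 3 months, which the plan accepts may raise missingness.
- **The affected figures are reported and used.** Protocol 4 and SAP 1 prefer Cox regression to weighting because it shows how covariates relate to OS. Those HRs have their own rows in the results shell: "Results from adjusted models in Appendix Table 3 will be based on multiple imputation via multivariate imputation by chained equations".
- **Adjustment of the treatment HR depends on these coefficients.** If they are too small, differences in LDH or ECOG between trial and Flatiron patients are only partly adjusted for.

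Neither optional sensitivity analysis in SAP 7.1 (extra covariates, time frame of initiation) would reveal the problem.

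**Working it through.** The plan gives no figure to reproduce on this point, so the design was simulated.

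**Inputs from the documents:** COLUMBUS ENCO+BINI n = 192 (Protocol 8.4); 40-60% missing (Protocol 4, SAP 1).

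**Assumed inputs**
- Flatiron: 60 ENCO+BINI and 450 comparator patients if ECOG is imputed (n = 702). If ECOG 0/1 is strictly required, half are dropped, leaving 30 and 225 (n = 447).
- True HRs: treatment 1.00, LDH 2.0, ECOG 1.6.
- Values missing completely at random, in Flatiron only.
- Four patterns of LDH-high and ECOG-1 prevalence, COLUMBUS vs Flatiron: 30 vs 42% and 28 vs 45% (trial modestly fitter); equal at 36% and 37% (balanced); 30 vs 50% and 28 vs 55% (trial much fitter); 42 vs 30% and 45 vs 28% (Flatiron fitter).
- 400 simulated studies per scenario, 10 imputations. Monte Carlo SE of the mean log-HR was 0.003-0.008.

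**Approximation.** Let f be the share of the pooled sample with imputed LDH. The fitted LDH HR is then about exp[(1 - f) × ln 2.0]. For example, with LDH only and 50% missing, f = 0.5 × 255/447 = 0.285, and exp(0.715 × 0.693) = 1.64.

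| Imputed | Missing in Flatiron | f | Approximation | Simulated LDH HR | 95% CI coverage |
|---|---|---|---|---|---|
| LDH only | 40% | 0.228 | 1.71 | 1.69-1.70 | 81-86% |
| LDH only | 50% | 0.285 | 1.64 | 1.62-1.65 | 73-79% |
| LDH only | 60% | 0.342 | 1.58 | 1.56-1.58 | 64-70% |
| LDH and ECOG | 40% | 0.291 | 1.64 | 1.63-1.65 | 55-66% |
| LDH and ECOG | 50% | 0.363 | 1.55 | 1.54-1.56 | 33-41% |
| LDH and ECOG | 60% | 0.436 | 1.48 | 1.46-1.48 | 14-21% |

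When ECOG is imputed, its HR falls from 1.6 to 1.40-1.41, 1.34-1.37 and 1.30-1.32 at 40, 50 and 60% missing.

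**Which omission causes it.** Adding only the outcome (death indicator and Nelson-Aalen hazard) gives an LDH HR of 1.95-2.03 with coverage of 93-97%. Adding only treatment and source leaves it at 1.46-1.72.

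**Dependence on assumptions.** With LDH only imputed at f = 0.29, the log-HR loss is 29% for a true LDH HR of 1.5 and 31% for 2.5. Coverage does depend on the true HR: at 1.5 and 50% missing it is 94% (LDH only) or 85% (both). A strong auxiliary predictor cuts the loss only from 28 to 24% (LDH only) or from 36 to 30% (both).

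**Treatment HR, ENCO+BINI vs comparator** (the direction worded in Protocol 8.7.4; Appendix Table 3 uses the reciprocal). Entries are ratios to the fit with no missing data, at 40/50/60% missing.

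| Pattern | LDH and ECOG imputed | LDH only |
|---|---|---|
| Trial modestly fitter | 0.975 / 0.966 / 0.959 | 0.994 / 0.991 / 0.989 |
| Balanced | 1.021 / 1.024 / 1.025 | 1.018 / 1.018 / 1.023 |
| Trial much fitter | 0.950 / 0.934 / 0.918 | 0.979 / 0.972 / 0.963 |
| Flatiron fitter | 1.071 / 1.082 / 1.098 | 1.044 / 1.051 / 1.059 |

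The balanced-group shift is not residual confounding. It vanishes when COLUMBUS has the same 50% missingness (0.990 vs 0.990). With outcome, treatment and source all added, the treatment HR is within 0.5% of the no-missing-data fit in all 24 scenarios. The treatment HR needs all three: with both imputed, trial modestly fitter and 50% missing, it is 0.964 as written, 0.978 with treatment and source, 0.977 with the outcome, 0.999 with all, and 0.998 with no missing data.

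**Cross-check.** A separately written simulation kept DAB+TRAM and VEM+COBI apart (relative sizes 192/40/300/60, LDH only imputed). The LDH HR was about 1.68, 1.61-1.62 and 1.54 at 40, 50 and 60% missing, and 1.98-2.02 once outcome and treatment were added. At 40% missing, DAB+TRAM vs ENCO+BINI moved from 0.990 to 0.974 when LDH was balanced, and from 1.003 to 1.021 with 30 vs 45% elevated LDH. Inverted, these are ratios of 0.990/0.974 = 1.016 and 1.003/1.021 = 0.982, the same signs as in the table.

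**The case against.** The MICE sentence is introduced as a short account of the general method, and the variable lists are given as examples. The programmed models may include OS. That is fair: this is a specification left unstated, not proof of an outcome-free analysis. But five places in the two documents speak only of baseline characteristics, and an analyst who follows them would leave the outcome out.

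The firm harm is to covariate HRs, which are neither an objective nor a decision rule. The treatment HR shift in the example above is |ln(0.964/0.998)| = 0.035, about a third of its SE of 0.098. The 8-10% shifts come from the most imbalanced patterns, which no passage supports. SAP 3.2 also says that the study is not powered for formal testing. All of this stands and limits the weight of the point.

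The sizes rest on assumed inputs. In particular, the LDH-only figures treat ECOG and LDH missingness as independent. If the two tend to be recorded together, patients with ECOG would have less missing LDH. At an assumed 20% missing, f = 0.2 × 255/447 = 0.114 and the LDH HR would be about exp(0.886 × 0.693) = 1.85. The loss is then smaller, but its direction is unchanged. The main simulation merges the two comparators. The cross-check shows that the point estimates hold with separate comparators, but coverage for a small VEM+COBI group was not examined.

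**Conclusion.** The concern holds. Followed as written, the plan attenuates the LDH HR, and ECOG's if missing ECOG is imputed. The log-HR loss roughly equals the share of patients with imputed values: about 23 to 45% at 40-60% missing in Flatiron, under the assumed group sizes. The direction was the same in every scenario run.

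The effect on the primary treatment HR is smaller and conditional: 0.6 to 9.8% over the assumed scenarios, and about 1% if only LDH is imputed and trial patients are modestly fitter. For ENCO+BINI vs comparator, the HR is too low when trial patients are fitter. It is too high when groups are balanced with missingness confined to Flatiron, or when Flatiron patients are fitter.

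This should be fixed before analysis, but it does not undermine the design. Confidence is high for the direction of the covariate attenuation and lower for the exact sizes.

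**What to change.** In Protocol 8.7.3 and SAP 6 and 7.1, with Protocol 4 and SAP 1 aligned, state:

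> Each imputation model for the OS analysis will include the death indicator and the Nelson-Aalen cumulative hazard at the observed time (or a Cox-compatible imputation method will be used), treatment group, data source, and every covariate in the adjusted Cox model. If PFS is compared, imputation for that analysis will use the PFS event indicator and cumulative hazard.

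Separately, reconcile the ECOG 0-or-1 inclusion criterion with the plan to impute missing ECOG. This decides whether the LDH-only or the LDH-and-ECOG figures apply.

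The cost is a wording change and a few columns already held in the data. With both covariates imputed, 50% missing and trial patients modestly fitter, the SE of the treatment log-HR rises from 0.098 to 0.100.
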